**Table 19. Analysis for MenABCWY Immune Response Secondary Objectives**

Stage of Study	Objective	Randomized Groups	Analysis Time Point	Analysis Population(s)	Strain/Serogroup	Analysis Endpoint
Stage 1	ACWY response after 1 dose of MenABCWY vs 1 dose of MenACWY-CRM	1 vs 2 and 3 vs 4	Visit 2 (post-Vaccination 1 blood draw)	Stage 1 mITT	MenA MenC MenW MenY	Subjects with hSBA titer $\geq 1:8$ (or LLOQ, whichever is higher) a for each strain
						Subjects with hSBA titer $\geq 1:4$ , $\geq 1:8$ , $\geq 1:16$ , $\geq 1:32$ , $\geq 1:64$ , and $\geq 1:128$ for each strain
						hSBA GMTs for each strain
	ACWY response after 2 doses of MenABCWY vs 1 dose of MenACWY-CRM	1 vs 2 and 3 vs 4	Visit 4 (MenABCWY, post-Vaccination 2 blood draw)	Stage 1 mITT	MenA MenC MenW MenY	Subjects with hSBA titer $\geq 1:8$ (or LLOQ, whichever is higher) for each serogroup
						Visit 2 (MenACWY-CRM, post-Vaccination 1 blood draw)
			hSBA GMTs for each serogroup			
	MenB response after 2 doses of MenABCWY vs 2 doses of bivalent rLP2086	1+3 vs 2+4	Visits 1 and 4 (baseline and post-Vaccination 2 blood draw)	Stage 1 evaluable immunogenicity, Stage 1 mITT	PMB80(A22) PMB2001(A56) PMB2948(B24) PMB2707(B44)	Composite response (proportion of subjects achieving an hSBA titer $\geq$ LLOQ for all 4 strains)
						Subjects achieving at least a 4-fold increase in hSBA titer from baseline for each of the 4 strains
						Subjects with hSBA titer $\geq$ LLOQ for each strain
Subjects with hSBA titer $\geq 1:4$ , $\geq 1:8$ , $\geq 1:16$ , $\geq 1:32$ , $\geq 1:64$ , and $\geq 1:128$ for each strain						
hSBA GMTs for each strain						

**Table 19. Analysis for MenABCWY Immune Response Secondary Objectives**

Stage of Study	Objective	Randomized Groups	Analysis Time Point	Analysis Population(s)	Strain/Serogroup	Analysis Endpoint	
	ABCWY response after MenABCWY vs MenACWY-CRM/bivalent rLP2086 at all blood sampling time points prior to booster dose (during Stage 1)	1+3 vs 2+4	Visits 1, 2, 3, and 4 (baseline, post-Vaccination 1 blood draw, Vaccination 2, post-Vaccination 2 blood draw)	Stage 1 evaluable immunogenicity, Stage 1 mITT	PMB80(A22) PMB2001(A56) PMB2948(B24) PMB2707(B44)	Subjects with hSBA titer $\geq$ LLOQ for each strain Subjects with hSBA titer $\geq$ 1:4, $\geq$ 1:8, $\geq$ 1:16, $\geq$ 1:32, $\geq$ 1:64, and $\geq$ 1:128 for each strain hSBA GMTs for each strain	
		1 vs 2 and 3 vs 4	Visits 1, 2, 3, and 4 (baseline, post-Vaccination 1 blood draw, Vaccination 2, post-Vaccination 2 blood draw)	Stage 1 mITT	MenA MenC MenW MenY	Subjects with hSBA titer $\geq$ 1:8 (or LLOQ, whichever is higher) for each serogroup Subjects with hSBA titer $\geq$ 1:4, $\geq$ 1:8, $\geq$ 1:16, $\geq$ 1:32, $\geq$ 1:64, and $\geq$ 1:128 for each serogroup hSBA GMTs for each serogroup	
Persistence	ABCWY response after MenABCWY vs MenACWY-CRM/bivalent rLP2086 at all blood sampling time points prior to booster dose (during Stage 2)	1+3 vs 2+4	Visits 1, 4, 7, 8, 9, and 10 (baseline, post-Vaccination 2 blood draw, antibody persistence blood draws 1-3, before booster vaccination)	Stage 2 mITT	PMB80(A22) PMB2001(A56) PMB2948(B24) PMB2707(B44)	Subjects with hSBA titer $\geq$ LLOQ for each strain	
		1 vs 2 and 3 vs 4	Visits 1, 4, 7, 8, 9, and 10 (baseline, post-Vaccination 2 blood draw, antibody persistence blood draws 1-3, before booster vaccination)	Stage 2 mITT	MenA MenC MenW MenY	Subjects with hSBA titer $\geq$ 1:8 (or LLOQ, whichever is higher) for each serogroup	

**Table 19. Analysis for MenABCWY Immune Response Secondary Objectives**

Stage of Study	Objective	Randomized Groups	Analysis Time Point	Analysis Population(s)	Strain/Serogroup	Analysis Endpoint
Booster	ABCWY response after MenABCWY booster dose	1+3 and 2+4	Visits 4, 10, and 11 (post-Vaccination 2 blood draw, before booster vaccination, postbooster blood draw)	Booster evaluable immunogenicity	PMB80(A22) PMB2001(A56) PMB2948(B24) PMB2707(B44)	Subjects with hSBA titer $\geq$ LLOQ for each strain
		1 vs 3	Visits 4, 10, and 11 (post-Vaccination 2 blood draw, before booster vaccination, postbooster blood draw)	Booster evaluable immunogenicity	MenA MenC MenW MenY	Subjects with hSBA titer $\geq$ 1:8 (or LLOQ, whichever is higher) for each serogroup

Abbreviations: ACWY = ACWY = *Neisseria meningitidis* group A, C, W, Y; GMT = geometric mean titer; hSBA = serum bactericidal assay using human complement; LLOQ = lower limit of quantitation; MenA = *Neisseria meningitidis* serogroup A; MenB = *Neisseria meningitidis* serogroup B; MenC = *Neisseria meningitidis* serogroup C; MenW = *Neisseria meningitidis* serogroup W; MenY = *Neisseria meningitidis* serogroup Y.

- a. The hSBA titer  $\geq$ 1:8 (or LLOQ, whichever is higher) is identical to hSBA titer  $\geq$ 1:8 since LLOQs for the ACWY serogroups have all been confirmed to be 1:8.

### **6.2.2. Secondary Safety Endpoints**

Safety endpoint data will be summarized according to vaccine received and reported in the ACWY strata based on prior vaccine history (see [Section 4.5](#)). The safety population at each corresponding analysis interval ([Table 6](#), [Table 7](#), and [Table 8](#)) will be used for the analysis of each endpoint. The secondary safety endpoints will be displayed for the Stage 1 safety populations in Groups 1 and 3.

Further statistical analyses will be performed on reactogenicity and AE data specified in the following sections to evaluate the safety profile of MenABCWY.

Listings may be provided by vaccine group and by vaccination.

#### **6.2.2.1. Local Reactions and Systemic Events**

Descriptive summary reports will be generated according to each vaccination (Vaccination 1, Vaccination 2, booster) and after any vaccination in Stage 1 and will be similarly displayed as the summary output described in [Section 6.1.2.1](#).

The difference in proportions of subjects (Group 1 – Group 3) who report any reaction or event and severe reactions or events reported after any vaccination in Stage 1 may be presented. The corresponding 2-sided 95% CI of the difference in percentages will be computed using the Miettinen-Nurminen method.

#### **6.2.2.2. Serious Adverse Events, Medically Attended Events, and Newly Diagnosed Chronic Medical Conditions**

Descriptive summary reports will be generated according to all of the analysis intervals defined in [Table 6](#) and will be similarly displayed as the summary output described in [Section 6.1.2.2](#).

Additionally, the differences in subjects in each vaccine group (Group 1 – Group 3) reporting at least 1 SAE, MAE, or NDCMC after any vaccination in Stage 1 may be summarized. The corresponding 2-sided 95% CI of the difference in percentages will be computed using the Miettinen-Nurminen method.

#### **6.2.2.3. Adverse Events**

Descriptive summary reports will be generated for AEs reported during the Stage 1 and booster vaccination phases (analysis intervals 1, 2, 3, 4, and 7 in [Table 6](#)) and will be similarly displayed as the summary output described in [Section 6.1.2.3](#).

The differences in subjects in each vaccine group (Group 1 – Group 3) reporting at least 1 AE during the Stage 1 vaccination phase may be summarized. The corresponding 95% CIs will also be computed using the Miettinen-Nurminen method.

#### **6.2.2.4. Immediate Adverse Events**

The number and percentage of subjects reporting AEs occurring within the 30-minute observation period immediately after vaccination will be summarized according to the analysis intervals defined in [Table 7](#). These summaries will include 95% Clopper-Pearson CIs.

Additionally, statistical analyses similar to [Section 6.2.2.3](#) will be conducted on subjects experiencing an immediate AE after any vaccination in Stage 1.

#### **6.2.2.5. School and Work Days Missed**

The total number of days a subject missed school and/or work will be descriptively summarized.

#### **6.2.2.6. Sensitivity Safety Analysis**

No sensitivity analyses are planned for safety data.

### **6.3. Exploratory Endpoints**

#### **6.3.1. Bivalent rLP2086 Immune Response Exploratory Objectives**

Subjects in the Stage 1 evaluable immunogenicity population will be used for analysis. hSBA titers obtained 1 month after Dose 1 (Visit 2) will be descriptively summarized. The 5 coprimary endpoints will be reported similarly to the primary immunogenicity endpoint ([Section 6.1.1](#)).

Additionally, the proportion of subjects with hSBA titer  $\geq$  LLOQ for each MenB strain as well as hSBA titers  $\geq 1:4$ ,  $\geq 1:8$ ,  $\geq 1:16$ ,  $\geq 1:32$ ,  $\geq 1:64$ , and  $\geq 1:128$  will be summarized similarly as described in [Section 6.2.1.1](#). Descriptive statistics on the GMTs as defined in [Section 5.2.2.1](#) will also be provided.

The hSBA GMTs for each MenB strain at Visit 11 will be summarized in Groups 2 and 4 combined for 1 month after the booster vaccination. See [Table 20](#).

**Table 20. Analysis for Bivalent rLP2086 Immune Response Exploratory Objectives**

Stage of Study	Objective	Randomized Groups	Analysis Time point	Analysis Population(s)	Strain	Analysis Endpoint
Stage 1	MenB response after 1 dose of bivalent rLP2086	2+4	Visits 1 and 2 (baseline and post-Vaccination 1 blood draw)	Stage 1 evaluable immunogenicity	PMB80(A22) PMB2001(A56) PMB2948(B24) PMB2707(B44)	Composite response (proportion of subjects achieving an hSBA titer $\geq$ LLOQ for all 4 strains)
						Subjects achieving at least a 4-fold increase in hSBA titer from baseline for each of the 4 strains
						Subjects with hSBA titer $\geq$ LLOQ for each strain
						Subjects with hSBA titer $\geq$ 1:4, $\geq$ 1:8, $\geq$ 1:16, $\geq$ 1:32, $\geq$ 1:64, $\geq$ 1:128 for each strain
						hSBA GMTs for each strain
Booster	MenB response after booster dose	2+4	Visits 4, 10, and 11 (post-Vaccination 2, pre-booster vaccination, postbooster blood draw)	Booster evaluable immunogenicity	PMB80(A22) PMB2001(A56) PMB2948(B24) PMB2707(B44)	hSBA GMTs for each strain

Abbreviations: GMT = geometric mean titer; hSBA = serum bactericidal assay using human complement; LLOQ = lower limit of quantitation; MenB = *Neisseria meningitidis* serogroup B.

### 6.3.2. Analysis for MenABCWY Immune Response Exploratory Objectives

Subjects in the booster evaluable immunogenicity population will be used for analysis. See Table 21.

**Table 21. Analysis for MenABCWY Immune Response Exploratory Objectives**

Stage of Study	Objective	Randomized Group	Analysis Time Point	Analysis Population(s)	Strain/Serogroup	Analysis Endpoint
Booster	ACWY immune response after booster dose	2 vs 4	Visits 4, 10, and 11 (post-Vaccination 2, pre-booster vaccination, postbooster blood draw)	Booster evaluable immunogenicity	MenA MenC MenW MenY	Subjects with hSBA titer $\geq 1:8$ (or LLOQ, whichever is higher) a for each serogroup
	ABCWY immune response after booster dose	1+3	Visits 4, 10, and 11 (post-Vaccination 2, pre-booster vaccination, postbooster blood draw)	Booster evaluable immunogenicity	PMB80(A22) PMB2001(A56) PMB2948(B24) PMB2707(B44)	hSBA GMTs for each strain
		1 vs 3	Visits 4, 10, and 11 (post-Vaccination 2, pre-booster vaccination, postbooster blood draw)	Booster evaluable immunogenicity	MenA MenC MenW MenY	hSBA GMTs for each strain

Abbreviations: ABCWY = ACWY = *Neisseria meningitidis* group A, B, C, W, Y; GMT = geometric mean titer; hSBA = serum bactericidal assay using human complement; LLOQ = lower limit of quantitation; MenA = *Neisseria meningitidis* serogroup A; MenC = *Neisseria meningitidis* serogroup C; MenW = *Neisseria meningitidis* serogroup W; MenY = *Neisseria meningitidis* serogroup Y.

- a. The hSBA titer  $\geq 1:8$  (or LLOQ, whichever is higher) is identical to hSBA titer  $\geq 1:8$  since LLOQs for the ACWY serogroups have all been confirmed to be 1:8.

#### 6.4. Additional Immunogenicity Analysis

Subjects who received prior polysaccharide meningococcal vaccine or subjects whose prior ACWY history is unknown are included in the mITT population as described in [Section 4.5](#). Additional sensitivity analyses of the secondary immunogenicity endpoints relating to MenA/C/W/Y strains described in [Table 19](#) may be performed by removing these subjects from the mITT population. Similar additional analyses may be done by removing from the analyses those subjects who received nonstudy meningococcal vaccines at any point between Visits 1 and 4.

An additional supportive analysis using the evaluable population (US and overall) is planned for the composite response (described in [Section 5.2.1.2](#)). For this supportive analysis, subjects with an assay titer < LLOQ for any of the 4 primary MenB strains will be defined as a nonresponder (composite response = 0) rather than have the status of missing.

Positive predictive value (PPV) analyses of secondary strain response for a given primary strain response within the primary strain subfamily will be performed at 1 month after the second vaccination using the evaluable immunogenicity population. For a specific time point, the PPV between a primary and secondary strain will be defined as follows: for the subjects who had titers  $\geq$  LLOQ for the primary strain, the percentage of subjects who have titers  $\geq$  LLOQ for the secondary strain. The calculation will require available data for both the primary and secondary strains.

Additional analyses may be performed to investigate the relationship of hSBA titers between the pre-booster dose time point and the post-booster dose time point for MenA, MenC, MenW, and MenY test strains separately for MenACWY-naïve and -experienced MenABCWY and Menveo groups. Scatterplots (with Pearson correlation coefficients) of pre-booster dose hSBA titers versus fold-rises from the pre-booster dose time point to the post-booster dose time point using the booster evaluable immunogenicity population will be provided. Similar analyses may be performed for Dose 1 and Dose 2 using the Stage 1 mITT population.

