MenABCWY (Groups 1 and 3 combined in Stage 2)	1 Month after the booster dose of MenABCWY (Visit 11)	PMB80 (A22), PMB2001 (A56), PMB2948 (B24), PMB2707 (B44)	Composite response (proportion of subjects achieving an hSBA titer \geq LLOQ for all 4 MnB strains) Proportion of subjects achieving at least a 4-fold increase in hSBA titer from baseline for each of the 4 MnB strains Proportion of subjects with hSBA titer \geq 1:4, \geq 1:8, \geq 1:16, \geq 1:32, \geq 1:64, \geq 1:128 for each MnB strain hSBA GMTs for each MnB strain
MenABCWY (Groups 1 and 3 separately in Stage 2)	1 Month after the booster dose of MenABCWY (Visit 11)	hSBA-MenA, hSBA-MenC, hSBA-MenW, hSBA-MenY	Proportion of subjects with hSBA-MenA/C/W/Y titer \geq 1:8, \geq 1:16, \geq 1:32, \geq 1:64, \geq 1:128 hSBA-MenA/C/W/Y GMTs
Bivalent rLP2086 + MenACWY-CRM (Groups 2 and 4 combined in Stage 2)	1 Month after the booster dose of bivalent rLP2086 + MenACWY-CRM (Visit 11)	PMB80 (A22), PMB2001 (A56), PMB2948 (B24), PMB2707 (B44)	Composite response (proportion of subjects achieving an hSBA titer \geq LLOQ for all 4 strains) Proportion of subjects achieving at least a 4-fold increase in hSBA titer from baseline for each of the 4 strains Proportion of subjects with hSBA titer \geq 1:4, \geq 1:8, \geq 1:16, \geq 1:32, \geq 1:64, \geq 1:128 for each strain hSBA GMTs for each strain

Abbreviations: GMT = geometric mean titer; hSBA = serum bactericidal assay using human complement; LLOQ = lower level of quantitation; MenA, MenB, MenC, MenW, and MenY = *Neisseria meningitidis* groups A, B, C, W, and Y; MnB = *Neisseria meningitidis* group B.

The exploratory analysis to investigate the association of the primary strains and additional MenB testing strains, as well as a sensitivity analysis that may be performed for immunogenicity in Stage 1, will be detailed in the SAP.

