**Table 1. Summary of Major Changes in SAP Amendments**

Version / Date	Associated Protocol Amendment	Rationale	Specific Changes
1 21MAR2017	Final, 16JAN2017	Original SAP	N/A
2 15FEB2018	Amendment 1, 23AUG2017	Protocol Amendment	
 
Updated the covariates for the subgroup analysis.
 
Updated to include the pilot safety population in the Stage 1 safety population.
 
Updated to remove the presentation of p-values in the safety summaries.
 
Added the requirement to perform mixed-effects model with repeated measures (MMRM)/generalized linear mixed-effects model with repeated measures (GLIMMIX) analyses on immunogenicity data.
 
Clarified the methods used in the noninferiority (NI) analyses. Added the criteria for NI analyses.
 
Added section for additional immunogenicity analyses.
 
Updated the derivation of age at vaccination to follow prior Trumenba® studies.
 

3 29OCT2018	Amendment 1, 23AUG2017	Regulatory input, Clarification Clinical team input	
 
Added sensitivity analysis for composite response to address regulatory request.
 
Clarified the modified intent-to-treat (mITT) population definition.
 
Added the lower limits of quantitation (LLOQs) for Neisseria meningitidis group A, group C, group W, and/or group Y (MenA/C/W/Y) assays and for secondary Neisseria meningitidis group B (MenB) strains.
 
Clarified race categorization in subgroup analyses.
 
Added planned positive predictive value (PPV) analyses for assessment of association between results for primary MenB and secondary MenB strains.
 
Added description of the variability assessment of ACWY data endpoints.
 
Removed previously included exploratory analyses.
 

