**Table 18. Analysis for Bivalent rLP2086 Immune Response Secondary Objectives**

Stage of Study	Objective	Randomized Groups	Analysis Time Point	Analysis Population(s)	Strains	Analysis Endpoint
Stage 1	MenB response after 2 doses of bivalent rLP2086	2+4	Visits 1 and 4 (baseline and post-Vaccination 2 blood draw)	Stage 1 evaluable immunogenicity, Stage 1 mITT	PMB80(A22) PMB2001(A56) PMB2948(B24) PMB2707(B44)	Subjects with hSBA titer $\geq$ LLOQ for each strain Subjects with hSBA titer $\geq$ 1:4, $\geq$ 1:8, $\geq$ 1:16, $\geq$ 1:32, $\geq$ 1:64, and $\geq$ 1:128 for each strain hSBA GMTs for each strain
			Visits 1 and 4 (baseline and post-Vaccination 2 blood draw)		PMB3175(A29) PMB3010(A06) PMB824(A12) PMB3040(A07) PMB1672(A15) PMB1989(A19) PMB648(B16) PMB866(B09) PMB1256(B03) PMB431(B15)	Subjects with hSBA titer $\geq$ LLOQ for each strain Subjects with hSBA titer $\geq$ 1:4, $\geq$ 1:8, $\geq$ 1:16, $\geq$ 1:32, $\geq$ 1:64, and $\geq$ 1:128 for each strain hSBA GMTs for each strain
Booster	MenB response after bivalent rLP2086 booster dose	2+4	Visits 4, 10, and 11 (post-Vaccination 2, pre-booster vaccination, postbooster blood draw)	Booster evaluable immunogenicity	PMB80(A22) PMB2001(A56) PMB2948(B24) PMB2707(B44)	Subjects with hSBA titer $\geq$ LLOQ for each strain

Abbreviations: GMT = geometric mean titer; hSBA = serum bactericidal assay using human complement; LLOQ = lower limit of quantitation; MenB = *Neisseria meningitidis* serogroup B.

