#### 6.5. Subset Analyses

Subgroup analyses may be performed on the primary and secondary immunogenicity (excluding analyses on the secondary MenB strains) and safety endpoints described in [Section 6.1](#) and [Section 6.2](#). No subgroup analyses are planned for rare events (endpoints with less than 1% of subjects in any group). Subgroups include age strata (10 to <18 years of age; 18 to <26 years of age), sex, race, ethnicity, and geographic location (US; ex-US). Race categories other than White, Black, or Asian will be combined into the “other” category for the analysis.

Additional exploratory or subset analyses to investigate the association of the primary and secondary MenB strains with demographic characteristics may be further explored.

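### The planned PPV at Visit 4 does not by itself show that a primary MenB strain predicts a secondary strain; SAP 6.4 should add the paired 2x2 contrast

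*SAP*

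**What the plan says.** Protocol 9.2.3 leaves to the SAP "The exploratory analysis to investigate the association of the primary strains and additional MenB testing strains". SAP Table 1 gives the purpose of the PPV in the version 3 entry: "Added planned positive predictive value (PPV) analyses for assessment of association between results for primary MenB and secondary MenB strains".

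SAP 6.4 specifies the analysis: "Positive predictive value (PPV) analyses of secondary strain response for a given primary strain response within the primary strain subfamily will be performed". For time point and population, it "will be performed at 1 month after the second vaccination using the evaluable immunogenicity population". The PPV is the percentage with a secondary-strain titer ≥ LLOQ among subjects with a primary-strain titer ≥ LLOQ, and "The calculation will require available data for both the primary and secondary strains". The section states no benchmark, threshold or decision rule for it.

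Two neighbouring passages do not fill the gap. The scatterplots and Pearson correlations in SAP 6.4 concern MenA, MenC, MenW and MenY titers, not MenB strains. SAP 6.5 says only that "the association of the primary and secondary MenB strains with demographic characteristics may be further explored", which is optional and about demographics.

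SAP 6.2.1.1 and Table 18 report each secondary strain's proportion ≥ LLOQ in the Stage 1 evaluable and mITT populations at "Visits 1 and 4 (baseline and post-Vaccination 2 blood draw"). Nothing ties these proportions to the PPV.

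**The concern.** The stated question is one of association: does response to a primary strain carry information about response to a secondary strain of the same subfamily? That needs a comparison of primary responders with primary nonresponders. The PPV uses responders only, so it contains no contrast. A secondary strain to which nearly everyone responds gives a high PPV against any primary strain, informative or not.

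What is at stake is how an exploratory table is read. There are 2 × 6 = 12 subfamily A pairs and 2 × 4 = 8 subfamily B pairs. A display of 20 PPVs offered as an assessment of association could be taken to show prediction when it shows only a high background response.

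**Working it through.** **Sample behind the PPV.** SAP 2.2.2 plans 150 US and 30 ex-US subjects assayed per subset, to yield 125 and 25 evaluable. With the protocol's 85% evaluable fraction (Protocol 9.1), 125/0.85 = 147.1 and 25/0.85 = 29.4, consistent with 150 and 30; 3 × 180 = 540 as stated. So each pair rests on about 150 evaluable subjects. The documents state no PPV value to reproduce.

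**Identity.** Let p be the proportion ≥ LLOQ for the primary strain, s that for the secondary strain, and q the secondary rate among primary nonresponders. Then s = p·PPV + (1 − p)·q, so

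PPV − s = (1 − p)·(PPV − q).

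If the strains are unrelated, PPV = q = s. If they are related, the PPV exceeds s by only a fraction (1 − p) of the responder-nonresponder difference. At p = 90%, a 20-point difference moves the PPV just 0.10 × 20 = 2 points above s.

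**Attainable range for fixed p and s.** max(0, (p + s − 1)/p) ≤ PPV ≤ min(1, s/p). Over all s, the width of this range is at most (1 − p)/p, and the excess over the no-association value is at most 1 − p (for p above one half).

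**Values of p from the documents.** Every 4-fold response as defined requires a titer ≥ LLOQ, so the Phase 2 4-fold rates in Protocol Table 12 are lower bounds for p at those planning figures: 90.1% for A56 and 82.3% for A22. The 72.9% composite bounds B24 and B44 from below.

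| Primary strain | p (at least) | Widest PPV range, (1 − p)/p | Largest excess over s, 1 − p |
|---|---|---|---|
| A56 | 90.1% | 0.099/0.901 = 11.0 points | 9.9 points |
| A22 | 82.3% | 0.177/0.823 = 21.5 points | 17.7 points |
| B24, B44 | 72.9% | 0.271/0.729 = 37.2 points | 27.1 points |

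A higher p narrows these further.

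**Against sampling error.** For A56, about 150 × 0.901 = 135 subjects are responders. A PPV of 115/135 = 85.2% has an exact (Clopper-Pearson) 95% CI of 78.1% to 90.7%, 12.7 points wide before rounding. That exceeds the whole attainable range.

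**Illustrations with assumed secondary rates** (the documents give none):

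| p | s | PPV if unrelated | Largest possible PPV |
|---|---|---|---|
| 95% | 90% | 90.0% | 94.7% |
| 90% | 85% | 85.0% | 94.4% |
| 80% | 75% | 75.0% | 93.8% |

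The last row is less severe. With 120 responders, 90/120 has a CI of 66.3% to 82.5%. About 7.5 of the 18.75 points above the no-association value (40%) fall inside it and 60% outside, so a PPV read against the overall rate can discriminate there.

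**Precision of the missing contrast.** Nonresponders number about 30 of 150 at p = 80%, 15 at 90% and 8 at 95%. Exact CIs are 59.5% to 98.3% for 13/15, and 47.4% to 99.7% for 7/8.

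**The case against.** The strongest reply is that most of the missing information is already planned. Table 18 gives each secondary strain's Visit 4 rate in the same evaluable population. With the counts that SAP 5.2 calls for in categorical summaries, a reader could subtract and rebuild most of the 2x2 table. This largely stands: the benchmark exists. But the PPV requires both results and Table 18 does not, so the reconstruction is exact only if no primary-strain result is missing, and nobody is told to make the comparison.

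A reader might infer more than the documents support, in four ways:

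- **That the PPV is the trial's evidence of breadth.** It is not. Breadth is assessed directly by a secondary objective, with proportions and GMTs for each of the 10 secondary strains. No threshold or claim hangs on the PPV.
- **That the PPVs will be high whatever the association.** This holds only where the secondary rate is high, and the documents give no secondary-strain rates.
- **That sampling error always swamps the signal.** The 80%/75% case shows otherwise.
- **That restricting the PPV to Visit 4 is a flaw.** All subjects are MenB-vaccine naive at Visit 1, so those sera address naturally acquired antibody, not how far a vaccine-induced response extends. Visit 4 is a reasonable choice.

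It is also fair that the proposed contrast is least precise where the PPV is least informative. That limits what can be learned about strains such as A56; it does not make the PPV a measure of association.

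**Conclusion.** The point holds as a limited one. The SAP's only specified measure of primary-to-secondary MenB association has no comparison group and equals the overall secondary-strain rate when the responses are unrelated. Where secondary response is high, a high PPV alone does not show prediction.

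The identity is exact. The bounds of 11.0, 21.5 and 37.2 points assume only that primary response is at least the Table 12 planning level. The individual PPV examples rest on assumed secondary rates.

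The analysis is exploratory. The five coprimary tests and the direct secondary-strain endpoints are unaffected.

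**What to change.** In SAP 6.4, for each within-subfamily pair at Visit 4, in subjects with both results, report:

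1. the four 2x2 counts;
2. the PPV with the secondary-strain rate in the same paired subjects beside it;
3. the secondary rate among primary nonresponders;
4. the difference between the two conditional proportions, with a 95% CI.

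Add a sentence saying that the PPV is read against the paired rate and not alone as evidence of association, and that the contrast is imprecise when few subjects are primary nonresponders. A Visit 1 table is optional and should be described as concerning naturally acquired antibody.

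The cost is a few table columns from results already planned: no new assays, subjects or alpha. The downside is wide intervals for high-response strains. SAP 3.5.2.2 refers to Stage 1 reporting in the past tense, so anything added now should be labelled post hoc.
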